That human migraine can be treated effectively with episodic injections of anti-CGRP antibodies begets the question whether these newly prescribe-able medications can be repurposed for other trigeminal pain conditions and the related glossopharyngeal cranial nerve pain which are known to involve neurogenic inflammation. Another pain condition with poor treatment options for sufferers is fibromyalgia, especially fibromyalgia with associated small fiber neuropathy which leads to systemic de-afferentiation of patients' sensory system. In this condition, there is strong evidence for presence of neurogenic inflammation, and it is a rational concept that neurogenic inflammation contributes to disease pathogenesis and especially to the dominating clinical symptom of pain.

We propose to treat patients (targeting enrollment of n=20) who suffer from trigeminal or glossopharyngeal nerve pain in the context of painful small fiber neuropathy. We predict that recruitment of these patients will not be a challenge in the PI's clinics, based on previous experience and ongoing referral practice. Primary criterion is to establish an excellent safety profile that recapitulates the favorable data recorded in migraineurs. The primary pain-related objective is reduction of pain and reduced use of rescue and other anti-pain medications.

Secondary pain-related objectives are improvement of circadian rhythm impairment by galcanezumab, improvement of serum markers for chronic inflammation including protein/peptide as well as small non-coding RNA molecules, and discovery of DNA polymorphisms that predispose treated patients to accentuated responses of either lack of response or particularly potent response.

Clinical Collaborators

[name] MD, Duke Neurology
[name] MD

Hypothesis/ Purpose

We hypothesize that the proposed galcanezumab regimen will be found safe in our patient population, and that provisional evidence of its effectiveness will become apparent. We envision galcanezumab to target neurogenic inflammation in the trigeminal territory and neurogenic inflammation associated with small fiber neuropathy/fibromyalgia.

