Before treatment, there will be a 4 week observation-only period, and another one 8 weeks post-treatment, so that the total study period will be 6 months.

We aim for 20 patients to be included in this study.

see more detailed graphics in the next section

In terms of ancillary, laboratory-based studies, we intend to draw blood before treatment and at the 45-, 75-, 105- and 135-day of treatment time-points. We will measure cytokine/chemokine/lipid pain- and inflammation markers in patients' serum, also determine microRNA in their serum, and genomic DNA polymorphisms, the latter only at baseline. Please see next section for more detail.

To establish safety of the anti-CGRP treatment in this patient cohort, blood draw at baseline and at the 45-, 75-, 105- and 135-days of treatment time-points will also include routine systemic sentinel/surveillance markers, namely comprehensive metabolic panel and complete blood count with differential, and complete urinalysis. No more than 45 ml of blood will be collected at any given visit.

In terms of additional safety parameters, we propose an open, patient-kept side-effect log, plus home-based recordings of blood pressure, heart rate and weight at a frequency of 2x/week.

We will set up a data and safety monitoring board for proper management and oversight of data handling and patient safety-related issue; see next section.

[figure not shown]
We expect to observe effective treatment, at least in a significant subgroup of patients. Effectiveness of treatment, also magnitude of any observed therapeutic effect will be correlated with the pain/inflammation proteinaceous, lipid and RNA-based biomarkers in patients' serum, also with any polymorphisms in the patients' genomic DNA.

We also expect galcanezumab treatment to show another record of safe treatment, our expectation sculpted by analysis of in-depth data from treatment of migraineurs. Yet we will remain vigilant and implement the proposed safety sentinel measures in order not to miss adverse effects. This appears prudent because trigeminal or glossopharyngeal nerve pain plus small-fiber neuropathy is a different underlying disorder than migraine, likely representing a higher prevalence in peri-menopausal female patients. We also believe it is likely that level of chronic pain suffering-associated stress will be higher in our study population than in migraineurs.

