Patients will be recruited via the PI's clinics at Duke University, the Duke Clinics that typically refer to her attention and outside clinics and providers that refer to her as well, and DEDUCE database. In case of slow recruitment patient self-help and patient advocacy associations in the facial pain arena will be informed of the ongoing study to assist with recruitment. These organizations (Facial Pain Research Foundations, Facial Pain Association) are well-known to the PI.

11) Brief Statistical Analysis Plan

Only patients who complete the study will be included in the statistical analysis.

Response to treatment will be assessed by comparing pain metrics during the 90-day treatment period vs averaged 30 day "run-in". Outcome variables will consist of selected readout parameters of "pain metrics", namely pain subjective rating on VAS (0-10) and medication co-use. Additional outcome variables include circadian rhythm-associated metrics. A daily readout for each variable will be entered into their log by each patient, or by automatic activity reads from their motion tracking device. In similar manner, we will compare pain metrics during the 90-day treatment period vs 60-day post-treatment observation.

We intend to conduct the study with an n=20 patients to successfully complete the study. This selected number appears the most feasible and practicable number. We are confident that with an n=20 we will be in a position to do justice to the objective of initial assessment of the safety of galcanezumab in the condition under study, trigeminal or glossopharyngeal pain in the context of painful small fiber neuropathy/fibromyalgia.

Following completion of the study, we will have estimates of effect sizes and corresponding 95% confidence intervals providing information on the precision of the statistical estimates of treatment effect. Power analysis will be performed based on these estimates and will provide us with guidance for sample sizes of follow-up studies that aim for demonstrating effectiveness.

The statistical analysis will be based on a linear mixed model for repeated measures. The

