time course of pain metrics reported during the treatment period will be compared with metrics during the run-in baseline. The covariance matrix describing the nature of correlations between repeated measures will be selected based on Akaike information criterion and Bayesian information criterion, as guided by our statistics software, SAS/STAT15.1. p-values <0.05 will be considered statistically significant. Effects of treatments will be investigated with the introduction of treatment as a binary covariate (we will evaluate the effects of pre- and post-treatment in two different models).

Patients' anti-pain treatment response will be correlated with blood markers for pain, inflammation and miRNA, and also for genomic markers. This approach will be pursued in order to identify candidate biomarkers that pre-dispose patients to experience an effective or non-effective treatment response. In case of recording any particular safety-related parameters, correlation of these markers to safety metrics will also be conducted. Association between molecular biomarkers and pain- and activity-related metrics will be evaluated (i) at each time point separately using a linear regression model; (ii) by modeling the association across all time points and including time covariate in the linear regression model. The ensemble of these approaches will help determine the periods when pain or activity-related metrics and molecular markers co-evolve and become highly correlated.

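### Twenty is given both as the number enrolled and as the number completing, and only completers are analysed: with any drop-out both figures cannot be met, and the analysed denominator is open to selection

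*Combined protocol and SAP*

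**What the plan says.** The number 20 appears in three places, attached to different counts.

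- Abstract: "targeting enrollment of n=20".
- Study Design / Overview: "We aim for 20 patients to be included in this study".
- Section 11, Brief Statistical Analysis Plan: "We intend to conduct the study with an n=20 patients to successfully complete the study".

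Section 11 also fixes who is analysed: "Only patients who complete the study will be included in the statistical analysis". It justifies the number on practical grounds ("This selected number appears the most feasible and practicable number") and expresses confidence that 20 patients are enough for an initial assessment of safety. Power is left for later: "Power analysis will be performed based on these estimates and will provide us with guidance for sample sizes of follow-up studies".

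The overview sets a run-in of 4 weeks, treatment of 12 weeks and follow-up of 8 weeks, "so that the total study period will be 6 months". The documents give no drop-out rate, no replacement rule and no enrolment figure above 20. They do not say whether completing means finishing treatment or finishing the whole period.

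**The concern.** Enrolled and completing are different counts, and they coincide only if nobody leaves a six-month study with a daily diary and five blood-draw time-points. The protocol does not itself assume that. Section 7 makes provision for patients who stop galcanezumab early because of an adverse event, and section 3 has the DSMB review recruitment and retention against goals, although no retention goal is stated.

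What is at stake is the denominator. Safety is the primary criterion, section 11 is the only analysis plan, and its population rule makes no exception for safety. Read literally, a patient who stops because of an adverse event and leaves the study is not analysed. The same rule shapes the pain result: if patients with little benefit leave more often, the completers' mean change overstates the effect. That estimate is also meant to guide the size of later studies.

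**Working it through.** **Inputs.** From the documents: 20 enrolled or included (Abstract; Study Design / Overview), 20 completing and a completers-only analysis (section 11). Assumed, because the documents give no figure: drop-out proportion d of 10%, 20% or 30%, independent between patients.

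**The plan's own figure.** The 20 cannot be reproduced by a formula. It is a feasibility number, with no effect size, standard deviation or power behind it. The 0.05 threshold in section 11 is not used to derive it.

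**Can both counts hold?** Expected completers from 20 enrolled are 20 × (1 − d). Enrolment needed for 20 completers is 20 / (1 − d), rounded up. The chance that all 20 complete is (1 − d)^20.

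| d | Completers of 20 enrolled | Enrolment for 20 completers | Chance all 20 complete |
|---|---|---|---|
| 10% | 18 | 22.2, so 23 | 12% |
| 20% | 16 | 25 | 1% |
| 30% | 14 | 28.6, so 29 | under 0.1% |

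At d = 0 both counts are 20. At any other value one of them fails.

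**Branch 1: enrolment stops at 20.** The cost is precision. For zero events in n patients, the upper end of the two-sided 95% Clopper-Pearson interval is 1 − 0.025^(1/n):

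- n = 20: 1 − 0.025^(1/20) = 16.8%
- n = 18: 1 − 0.025^(1/18) = 18.5%
- n = 14: 1 − 0.025^(1/14) = 23.2%

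For a simple mean change per patient, the 95% half-width in standard-deviation units is t(0.975, n − 1)/√n. This gives 0.468 at n = 20, 0.497 at 18, 0.533 at 16 and 0.577 at 14. At 20% loss the interval is 0.533/0.468 = 1.14 times as wide. This is a guide only, since the planned model is a mixed model on repeated diary data.

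**Branch 2: enrolment continues until 20 complete.** The nominal limit stays at 16.8%, but it describes patients who stayed. At 20% loss, 25 are treated and 5 leave. Suppose k of those 5 left because of an event that no completer had. The completers show 0/20 whatever k is, while all treated patients show k/25: 4% for k = 1 and up to 20% for k = 5.

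So the first branch costs precision, and in both branches the analysed group is selected.

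**The case against.** The strongest reply is that the overview statements are aims, not caps. The word for patients included is looser than enrolled, section 11 is the more specific text, and sections 8 and 10 describe good access to patients with further recruitment routes in reserve. On that reading 20 completers governs and enrolment simply goes above 20. This stands in part. A reader might infer that the analysed number must fall below 20, and the documents do not support that: it follows only if enrolment stops at 20 and someone leaves. What remains is that no passage says which count governs.

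A reader might also infer that the adverse events of patients who leave are lost. That is not supported either. Section 7 has all adverse events after consent recorded on the case report form, and section 3 gives the DSMB cumulative adverse-event data, neither limited to completers. Most analyses described in section 11 concern pain, medication use, circadian measures and biomarkers. The problem is the analysed denominator, not safety reporting.

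Third, no power or precision claim is damaged, because none is made. The zero-event limits are an illustration that the plan does not specify, and they depend on convention: a one-sided 95% bound, 1 − 0.05^(1/n), is 13.9% at 20 and 19.3% at 14.

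Finally, the completers-only rule would still be a weakness if 20 were stated consistently. That is true. The two belong together here because the rule is what makes the choice of count matter for the analysis.

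**Conclusion.** The point holds as one of consistency and analysis population. It is not an arithmetic error. The same 20 serves as the enrolment target and as the completer number, and unless nobody leaves, one of the two must give way.

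The size of the mismatch is 2 to 6 fewer patients analysed, or 3 to 9 more enrolled, at an assumed loss of 10% to 30%. For a single-arm pilot sized on feasibility, the loss of precision is modest. The selection matters more, because it touches the primary safety criterion and the pain estimate, and enrolling more patients does not remove it.

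This rests on three assumptions: the drop-out range, that the completers-only sentence covers safety (its wording is general), and that a patient who stops treatment early does not count as a completer. The last cannot be settled while completion is undefined.

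**What to change.** 1. State one governing number in the Abstract, the Study Design overview and section 11. One option is 20 patients enrolled and treated. If 20 completers is the real target, give the enrolment number with the assumed drop-out (for example 25 at 20%) or a replacement rule.
2. Define completion: the end of the treatment period or the end of post-treatment observation.
3. Replace the completers-only sentence in section 11. Summarise safety in all patients who receive at least one dose. Fit the planned mixed model to all available diary data from all treated patients, which it can do with incomplete follow-up if the missing data can be taken as missing at random given the observed data. Report completers as a sensitivity analysis, and give the number who leave and their reasons.

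The cost is a few sentences in three places and a little more analysis work. The pain estimates may be slightly less favourable than among completers alone. No added patients or visits are needed if 20 treated is the number chosen.

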Treatment with a CGRP-neutralizing antibody, galcanezumab in this specific patient group, being seen in the PI's clinics on a regular basis, is rooted in the rationale of unmistakable presence of clinical signs of neurogenic inflammation in the painful territory, such as episodic swelling combined with redness/hyperemia, also relief by external cold application which typically patients with trigeminal or glossopharyngeal nerve pain abhor.

Primary Outcome Measures

Primary criterion is to establish an excellent safety profile that recapitulates the favorable data recorded in migraineurs. The primary pain-related objective is reduction of pain and reduced use of rescue and other anti-pain medication.

Inclusion Criteria

- G50.1 diagnosis (can encompass an add-on G50.0 and other headache G43.... codes), or G52.1 diagnosis code (with explicit mentioning of pain of glossopharyngeal origin) **AND** small fiber neuropathy diagnostic codes G63.3, G60.8, G62.8 (can encompass fibromyalgia diagnostic code M79.7)
- 18-80 years old
- not allergic to galcanezumab and other hu mAb biologics

Exclusion Criteria

- allergic to galcanezumab and other hu mAb biologics
- pregnancy

Study Design / Overview

We propose to treat patients open label for 12 weeks, with galcanezumab, supplied by Eli Lilly, as add-on to all other therapeutic measures. We propose to use a 240mg/120mg/120mg regime, with subcutaneous (self-)injections every 4 weeks.

To reflect pain experienced by patients, the primary read-out is pain level on a 0-10 visual analog scale. We will be prompting patients to record a daily summary read at the end of each day.

[figure not shown]
The second criterion is reduction of intake of anti-pain medication (rescue PRN or regular) which the patients will record.

Chronic pain, especially fibromyalgia pain combined with trigeminal or glossopharyngeal nerve pain, is a potent disruptor of circadian rhythm. We strongly believe that this is an important and hitherto under-appreciated contributor to individual disease burden. Therefore, the third criterion is assessment of circadian rhythm function. We will assess this by having the patient rate subjectively how energetic they feel during awake day-time. Wearable activity monitors will be used to address how many hours patients sleep per

24h period, with detailed focus on total duration of sleep/rest and duration of night-time sleep only.

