We also expect that the proposed studies will be very important for guiding future, more in-depth studies involving larger patient cohorts, placebo-controlled/double-blinded studies, which will possibly lead us toward a personalized-medicine approach.

Study Design Detail

1) Schedule of Activities over Time

2) Blood draw: detailed analysis

Before treatment, and at 45th, 75th, 105th and 135th day of treatment, we propose to assess the following blood parameters, related to pain-associated biomarkers in the systemic circulation.

For this, we propose to study cytokine/chemokine pain- and inflammation markers in patients' serum, using commercially available protein multiplex detection assays. In serum, the following 39 cytokines/chemokines/lipid mediators/peptides will be measured: EPO, GM-CSF, IFN- γ , IL-1 β , IL-2, IL-4, IL-5, IL-6, IL-9, IL-10, IL-12/IL-23p40, IL-12p70, IL-13, IL-15, IL-16, IL-17A, IL-17A/F, IL-17C, IL-17E/IL-25, IL-17F, IL-21, IL-22, IL-23, IL-27p28/IL-30, IL-31, IL-33, IP-10, KC/GRO, MCP-1, MIP-1 α , MIP-1 β , MIP-2, MIP-3 α , TNF- α , VEGF-A, TGF- β , CGRP, Resolvin-D1, Prostaglandin-E2. For these measurements, we will be using a human 35-plex ELISA (U-PLEX Biomarkers) and single ELISAs (Signosis; Cayman).

These are key mediators and indicators of pain and inflammation. We believe it will be feasible to conduct these assays. For each marker there is sufficient evidence supporting its role in pro-algesic inflammation or organismal response to tissue damage. We are

convinced that their ensemble will prove a powerful source of mechanistic data that will elucidate treatment responses to galcanezumab in our patient population.

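### Follow-up sample sizes are to be based on uncontrolled within-patient changes, which do not estimate the drug-minus-placebo difference a placebo-controlled trial needs; such a trial is likely to be too small unless the estimate is discounted or replaced.

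*Combined protocol and SAP*

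**What the plan says.** The Study Design / Overview section describes the design: "We propose to treat patients open label for 12 weeks, with galcanezumab, supplied by Eli Lilly, as add-on to all other therapeutic measures". No concurrent control is described anywhere.

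Section 11 (Brief Statistical Analysis Plan) defines treatment response by "comparing pain metrics during the 90-day treatment period vs averaged 30 day" run-in. It then adds a second contrast: "we will compare pain metrics during the 90-day treatment period vs 60-day post-treatment observation". Both are within-patient, and only patients who complete the study are analysed. The model term for treatment is a period indicator: "Effects of treatments will be investigated with the introduction of treatment as a binary covariate", with the pre- and post-treatment comparisons fitted in two separate models.

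On the use of the results, section 11 says "we will have estimates of effect sizes and corresponding 95% confidence intervals providing information on the precision", and then "Power analysis will be performed based on these estimates and will provide us with guidance for sample sizes of follow-up studies". The follow-up studies meant there are those aimed at demonstrating effectiveness. The end of the overview says what future work is expected: "future, more in-depth studies involving larger patient cohorts, placebo-controlled/double-blinded studies".

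**The concern.** The power analysis for a placebo-controlled trial needs the difference between drug and placebo. This pilot can estimate only the change between periods in patients who all know they are on active drug and who rate their own pain from 0 to 10. That change combines any drug effect with placebo response, natural course and other time effects. The on/off-treatment indicator cannot separate them, because treatment is fully confounded with time.

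The documents mention neither placebo response nor time trend, and they describe no discount on the estimate and no planning on a confidence limit. Restricting the analysis to completers probably pushes the same way, since patients who stop for lack of benefit leave the estimate.

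At stake is the use section 11 names for the effect estimates beyond describing their precision. A target difference that is too large gives a follow-up trial that is too small to show a real but smaller drug effect.

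**Working it through.** **Inputs from the documents.** Open label, no control arm (overview). Contrasts of the 90-day treatment period with the 30-day run-in and with the 60-day post-treatment period; 20 completers, a number chosen for feasibility; significance at 0.05, sidedness not stated (section 11). No effect size, SD, target power, placebo response or follow-up sample size is given, so there is no calculation of the plan's own to reproduce.

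**Assumptions.** Two-sided 0.05, 80% power, 1:1 allocation, the same SD of change in both arms. D is the observed change from run-in, and f is the share of D that a placebo arm would also show. For illustration, D = 2.0 points and SD = 2.5.

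**Step 1: size ratio.** Per arm, n = 2[SD(1.96 + 0.84)/Δ]². The plan's input is Δ = D. The difference the trial must detect is D(1-f). The ratio of needed to planned size is therefore 1/(1-f)², whatever D, SD, alpha and power are.

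**Step 2: true power of a trial planned on D.** Power ≈ Φ[(1-f) × 2.80 - 1.96].
- f = 0.10: Φ(0.56) = 71%
- f = 0.25: Φ(0.14) = 56%
- f = 0.50: Φ(-0.56) = 29%

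Rounding n up to a whole number of patients moves the first figure to 72%.

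**Step 3: illustration.** Planned on the full change, n = 2(2.5 × 2.80/2.0)² = 24.5, so 25 per arm.

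| f | ratio | needed per arm | true power with 25 per arm |
|---|---|---|---|
| 0 | 1.00 | 25 | 81% |
| 0.10 | 1.23 | 31 | 72% |
| 0.25 | 1.78 | 44 | 56% |
| 0.40 | 2.78 | 69 | 40% |
| 0.50 | 4.00 | 99 | 29% |

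With SD = 2.0 and the t distribution, the planned size is 17 per arm; 29 are needed at f = 0.25 and 64 at f = 0.50. The power losses are the same, 56% and 29%. The absolute sizes depend on the assumed SD; the ratios do not.

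**Step 4: sampling error of the pilot.** With n = 20 the 95% CI half-width is t(0.975; 19 df)/√20 = 2.093/4.472 = 0.468 SD. For D = 2.0 and SD = 2.0 the interval is 2.0 ± 0.94, or 1.06 to 2.94. The lower limit implies 57 per arm and the upper about 9, so sampling error works in both directions.

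A simulation of 200,000 pilots (D = 2.0, SD = 2.5) gave the chance that the planned size falls below the needed size:

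| f | planned on the point estimate | planned on the lower 95% limit |
|---|---|---|
| 0 | 52% | 7% |
| 0.25 | 80% | 18% |
| 0.40 | 92% | 31% |
| 0.50 | 96% | 42% |

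**Step 5: the second contrast.** The comparison with the post-treatment period is also uncontrolled, but its biases differ. Continued natural improvement, or drug effect persisting after the last dose, would shrink it. The formula in step 1 applies to the run-in contrast and does not give a direction for this one.

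**The case against.** The strongest reply is that section 11 offers guidance, not a rule. It does not say that the point estimate will be taken unadjusted as the between-arm target, and it promises confidence intervals. Planning on the lower limit would remove much of the shortfall: in the SD = 2.0 example, 57 per arm would still have about 75% power at f = 0.50. This stands in part. But the plan does not commit to the lower limit, and a confidence interval describes sampling error around the before-after change, not the gap between that change and the drug-minus-placebo difference.

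A reader might infer that the follow-up trials would necessarily be too small, or that the before-after change is an upper bound on the drug effect. The documents support neither. They give no placebo response, and at f = 0 there is no bias towards too small a trial. Some forces act the other way: reduced use of pain medication is itself an outcome and could mask a fall in pain, and entry requires no minimum pain score, so regression to the mean is not built in by a threshold. The absence of a threshold does not, however, remove placebo response.

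It is also fair that only later trials are affected, and that these would need their own sample-size justification.

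**Conclusion.** The mismatch between what the pilot estimates and what a placebo-controlled trial needs follows from the text alone and rests on no assumed number. Its consequence is conditional. If a share f of the change from run-in is non-specific, the needed size is 1/(1-f)² times the planned size, and nominal 80% power falls to about 72%, 56% and 29% at f = 0.10, 0.25 and 0.50. Because f, D and SD are all assumptions, the shortfall is likely but not shown. Avoiding it requires f to be zero, an offsetting bias, or an adjustment that the plan does not describe. The point concerns the planning output of the pilot; its conduct, its safety objective and its analysis are not affected. The change is worth making because it is cheap.

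**What to change.** Replace the power-analysis sentence in section 11 with one or two sentences saying that:
- the pilot supplies the SD of the phase means and of their change, the within-patient correlation, diary completeness and drop-out for planning;
- the between-arm target difference for a controlled follow-up trial will be set from a clinically important difference stated in advance;
- the before-after change, from either contrast, will not be used undiscounted as that target.

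The value of the important difference, and of any discount, can be left to the follow-up protocol, since these documents support no figure for either. Requiring the lower confidence limit on top of a discount is optional.

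The cost is the redrafting and a less favourable planned size for the follow-up trial. No extra patients, visits or data are needed in this study.

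### The pain model neither secures a patient-level treatment effect nor states its unit of analysis; on daily ratings its 95% confidence intervals may be too narrow if response varies between patients

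*Combined protocol and SAP*

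**What the plan says.** Section 11 compares 90 treatment days with a 30-day run-in, and separately with 60 post-treatment days, in 20 completers. For the first comparison, the "time course of pain metrics reported during the treatment period will be compared with metrics during the run-in baseline". The model is a repeated-measures linear mixed model. On covariance: "The covariance matrix describing the nature of correlations between repeated measures will be selected based on Akaike information criterion and Bayesian information criterion". On treatment: "Effects of treatments will be investigated with the introduction of treatment as a binary covariate", with the note that "we will evaluate the effects of pre- and post-treatment in two different models". The threshold is "p-values <0.05 will be considered statistically significant".

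No random effect, candidate covariance structure, degrees-of-freedom method or robust standard error is named. The unit of analysis is open: the section describes the run-in as averaged, but also describes a daily log entry for each variable.

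The output is to be "estimates of effect sizes and corresponding 95% confidence intervals providing information on the precision of the statistical estimates of treatment effect", followed by: "Power analysis will be performed based on these estimates and will provide us with guidance for sample sizes of follow-up studies".

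The same section aims to "identify candidate biomarkers that pre-dispose patients to experience an effective or non-effective treatment response". The Abstract, the Study Design / Overview section and the blood-draw section (Study Design Detail, 2) likewise expect benefit in at least a subgroup, with strong responders and weak or non-responders. No size is given for this variation.

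**The concern.** If patients truly differ in how much they change, the mean change across 20 patients carries a variance of tau²/20 that no number of daily ratings can reduce. A random intercept does not represent this term, because it cancels in the within-patient contrast. An AR(1) residual absorbs little of it: with a random intercept and tau of 1.0, the fitted autocorrelation rises only from 0.50 to 0.54. A model with one common treatment coefficient and such a covariance therefore treats many days as if they could stand in for many patients.

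Differences in response are the protocol's own premise. The biomarker correlations make use of them but do not change the standard error of the main pain estimate. What is at stake is the honesty of the intervals and the variance passed to the follow-up power analysis.

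**Working it through.** **Inputs.** From section 11: 20 patients, periods of 30, 90 and 60 days, 95% intervals, 5% level (two-sided assumed). Not in the documents, and assumed here: between-patient SD 1.5, daily within-patient SD 1.5, autocorrelation rho 0.3–0.7, tau 0 to 1.5 points. In the main scenario each patient has an even chance of no change or an improvement of 2·tau. The SD of change is then tau, the mean effect is tau, and nobody worsens. The plan has no figure to reproduce: n=20 rests on feasibility, with no effect size, SD or power.

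**Closed form.** True SE² = (SE without heterogeneity)² + tau²/20. At rho 0.5 the first SE is 0.116.
- tau 0.5: √(0.01346 + 0.0125) = 0.161
- tau 1.0: √(0.01346 + 0.05) = 0.252
- tau 1.5: √(0.01346 + 0.1125) = 0.355

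Random intercept + AR(1), fitted by REML, reports mean SEs of 0.118, 0.125 and 0.137. Expected non-coverage is 2·(1 − Φ(1.96·SE_model/SE_true)) = 15%, 33% and 45%. Simulation gave 13.4%, 35.6% and 46.0%. At tau 0 the same model gave 4.2%, which isolates the cause.

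**Simulated non-coverage of the nominal 95% interval, %** (ranges over rho; treatment v run-in unless stated)

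| Reading | tau 0 | 0.5 | 1.0 | 1.5 |
|---|---|---|---|---|
| Daily, random intercept + AR(1) | 4–6 | 11–19 | 26–39 | 41–53 |
| Same, treatment v post-treatment | 5–7 | 11–27 | 34–50 | 42–62 |
| Daily, AR(1) alone | 0–2 | 2–4 | 13–14 | 23–28 |
| Daily, ARMA(1,1) | 1–4 | 3–8 | 10–21 | 24–31 |
| One averaged run-in record + 90 daily, rho 0.3 | 0 | 0 | 2 | 9 |
| Same, rho 0.7 | 8 | 8 | 15 | 27 |
| Random treatment effect on the AIC menu | 3–5 | 7–8 | 5–6 | 5–6 |
| Four 30-day blocks; CS, AR(1) or unstructured by AIC/BIC | – | 9–12 | 7–12 | 7–12 |
| Random treatment effect pre-specified, 19 df | 2–4 | 4–6 | 4–6 | 4–6 |
| Paired t-test on patient period means | 3–7 | 3–7 | 3–7 | 3–7 |

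There were 300 to 1,000 trials per setting; Monte Carlo error is about 1–2 points.

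**Robustness** (random intercept + AR(1), rho 0.5; tau 0.5, 1.0, 1.5). With t on 19 df: 10.1, 33.0, 43.7%. With ratings rounded and cut to 0–10: 12.7, 34.3, 47.7%. With normally distributed responses around a zero mean: 14.2, 35.5, 46.0%.

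**Does the selection rule protect?** An unstructured matrix over 120 days needs 120·121/2 = 7,260 parameters, against 20·120 = 2,400 ratings. From a menu of CS, AR(1), ARMA(1,1) and random intercept + AR(1), AIC and BIC each choose the last in 95–100% of trials. That is partly by construction, since the data were generated with patient intercepts and AR(1) errors. With a random treatment effect added, both choose it in 98–100% of trials at tau 1.0 or more. At tau 0.5, AIC does so in only 42–86% and BIC in 24–76%.

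**Follow-up illustration** (assumed: difference 1 point, 80% power, two-sided 5%, SD back-calculated as SE·√20; n per arm = 2·(1.96 + 0.8416)²·SD²).
- SE 0.125: SD 0.559, 15.70·0.3125 = 4.9, so 5 per arm
- SE 0.246 (close to the true value at tau 1.0): SD 1.100, 15.70·1.210 = 19.0, so 19 per arm

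**The case against.** The strongest reply is that the model with the worst figures is not in the plan. Section 11 names neither a random intercept nor AR(1). A patient-level treatment effect is itself a covariance structure, and the text does not exclude it from the AIC/BIC choice. A reader might infer from the table that the plan's intervals fail 26–53% of the time. The documents do not support that: those rates belong to one reading and to assumed values of tau, the SDs and rho.

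There are also benign readings. If the averaged run-in means one mean per period per patient, the mixed model equals the paired t-test and the problem disappears. Monthly blocks need only 4·5/2 = 10 unstructured parameters. Even on daily data, AR(1) alone is conservative at small tau.

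A reader might also infer an inflated false-positive rate. That requires a zero mean effect with real heterogeneity, so that some patients worsen, and the protocol does not predict this. In the main scenario the mean effect is not zero, and the paired t-test is itself significant in 69–90% of trials at tau 0.5 and 93–98% at 1.0. The p-value is therefore secondary to interval width.

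Finally, safety is the primary criterion, no decision rule uses this p-value, and the later studies are envisaged as placebo-controlled, so this standard error would not be their only planning input.

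All of this limits the size of the point but does not remove it. Daily recording and the comparison of time courses make daily ratings a natural reading. Whether the intervals are valid then depends on a menu and a unit of analysis that the plan leaves unstated.

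**Conclusion.** The point holds in conditional form. On daily ratings, with tau of 1.0 point and the other assumed inputs, the nominal 95% interval misses about 13–14% of the time under AR(1) alone and 26–39% under random intercept + AR(1). The problem is small or absent if tau is small, if a random treatment effect is on the AIC menu (about 5–8% for tau above 0), or if one mean per period per patient is analysed; monthly blocks with an unstructured option leave about 7–12%.

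The direction follows from the design: 20 patients, many days each, and expected differences in response. The size rests entirely on values that the documents do not give. Bias in the estimate is not claimed. Severity is low to moderate, and the change is a cheap improvement to the main pain read-out.

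**What to change.** State in section 11 whether daily ratings or period means are analysed, and list the candidate covariance structures. Then do one of the following:

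- make the pain estimate a paired analysis of each patient's treatment-period mean minus run-in mean, with the daily model as support; or
- pre-specify, outside the AIC/BIC selection, a patient-level random treatment (period) effect with Kenward-Roger degrees of freedom.

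Apply the same choice to treatment versus post-treatment. Report the patient-level SD of change and use it for follow-up planning.

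The cost is about three sentences in the plan and, for the second option, one RANDOM statement; no new data are needed. The downside is wider intervals and, for the random-effect model, a slightly conservative test (about 2–4% in place of 5%) if response does not vary.
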